## 5 Participant Selection

Approximately 300 smokers will be recruited from the Multiethnic Cohort (MEC) study or the general population in Hawai'i. 100 participants from each of the three designated ethnic/racial groups with equal distribution by gender. All participants will be recruited from Hawai'i to reduce variation due to geographical location and maximize our ability to recruit the targeted ethnic/racial groups. Based on the data collected from the MEC, participants who are at least 21 years old and who currently smoke greater than 5 cigarettes per day (current smokers) will be selected and contacted in the MEC standard method by sending a letter inviting them to participate in this study. The letter states that a researcher will be in contact with them to provide further information and obtain verbal consent to submit to the telephone screening questionnaire, if interested. In the MEC database, the approximate number of Oahu participants that might be available for each of the three categories of participants is listed in Table 2. From past experience with Oahu MEC participants, including smokers we expect a participation rate of ~50%. Several hundreds of additional MEC current smokers are also available from the neighboring islands.

**Table 2.** Number of potential Oahu MEC participants available for each category.

Race/ethnicity	Smokers*
Japanese Americans	810
Non-Hispanic Whites	397
Native Hawaiians	385

\* As determined from the most recent follow-up questionnaire

Recruitment beyond the MEC sample will be expanded to the general population of smokers in Hawai'i. Recruitment will be conducted via local print, radio, TV, or internet advertisements and posted flyers.

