**Project 3: Ethnic/Racial Differences in metabolism and DNA Adduct Formation by****1,3-Butadiene**

**Aim 1:** This Aim concentrates upon a subset of the participants recruited in the Clinical Core (the 100 smokers from each of three ethnic groups) with the objective being to characterize differences in metabolites of 1,3butadiene as well as DNA adduct formation by race/ethnicity. Levels of metabolites and of DNA adducts of 1,3-Butadiene will be compared between Japanese-Americans, Native Hawaiians, and non-Hispanic Whites. Adjustments for age, sex, TNE, CPD, and BMI will be performed using the “LS means” option in Proc GLM in SAS. Prior to model-fitting we will examine QC metrics and estimate laboratory variation in the outcomes based on duplicate samples from the same individual and time period. We will identify batch effects and individual outliers. If required, polynomial or log transformations will be used to normalize the distribution of metabolite and DNA adduct levels prior to analysis. With 100 smokers from each of the three groups we will have 80 percent power to detect a difference between any two ethnic groups in these outcomes which amounts to approximately 6 percent of the total variance of the outcome. Here we correct (using the Bonferroni method) for making 3 such comparisons by requiring  $p < .017$  in order for any single comparison to be declared significant.

**Aim 2:** This aim investigates the association between urinary butadiene DNA adducts and lung cancer risk among White and African-American participants (smokers) in project 1. One hundred cases and one hundred controls for each ethnic group will be assessed. Controls will be frequency matched to the cases by age and sex. The primary issue is whether DNA adducts convey independent information beyond that which is contained in smoking dose, either self-reported (CPD) or measured (TNE). We will utilize unconditional logistic regression to evaluate the association between risk and DNA adducts after including CPD and TNE into the models. With 200 cases and 200 controls total (pooling both ethnicities) in this analysis we will be able to detect a 2.25 fold lung cancer risk difference between the highest and lowest quintiles of the distribution of DNA adducts using a test for log-linear trend. Effects specific to a single ethnic group must be larger (3-fold between top and bottom quintiles) than this to be detectable.

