**Aim 1:** Evaluation of ethnic differences in DNA adducts in oral cells quantified in 100 smokers from Core B in each of three ethnic groups. This aim will quantify DNA adducts of acrolein, crotonaldehyde, NNN, NNK, and formaldehyde and identify ethnic differences in levels of these adducts. After QC, outlier identification, analysis of duplicate samples for laboratory variation and batch effects we will fit linear regression models to the (possibly log or power-transformed) adduct levels to allow for differences by age, sex, BMI, TNE and CPD while examining ethnic group differences. The SAS procedure GLM will be used to provide adjusted means (LS means) and to test for the significance of the observed ethnic differences in those means.

As in Project 3, Aim 1, for a given outcome (DNA adduct) we will have 80 percent power to detect a difference between any two ethnic groups which amounts to approximately 6 percent of the total variance of a given outcome. We can also examine the joint effects of smoking and ethnicity in the total of 300 Core B participants and will have 80 percent power to detect ethnicity x smoking interactions that explain at least an additional 1 percent of variation for any outcome.

**Aim 2:** There are two sub aims to Aim 2. The first is to compare urinary metabolites in both smokers and nonsmokers in the three ethnic groups. The main hypothesis is that acrolein and crotonaldehyde metabolites, as well as metabolites from oxidative damage and

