inflammation are higher in Native Hawaiian non-smokers than in the other 3 ethnic groups, and that this is the reason that acrolein and crotonaldehyde metabolites were higher in Native Hawaiian smokers than Japanese American smokers in our published study. We will also compare the levels of the urinary metabolites in the smokers from the three ethnic groups. We will also compare smokers to non-smokers from each ethnic group (for metabolites of acrolein, and crotonaldehyde and biomarkers of oxidative damage and inflammation). Sub aim 2 is to relate DNA adducts measured for the 300 participants in Core B to urinary metabolites of TNE, total NNAL, mercapturic acids of acrolein, and crotonaldehyde measured in the same individuals. After QC, examinations of batch effects and laboratory variation, outlier detection, transformation to normality, we will estimate the ethnic differences and provide linear regression estimates of the relationships between the DNA adducts and metabolites. For sub aim 1 we will compare the urinary metabolite levels in each group of 100 with the other groups. We will use a p-value for any pairwise comparison of 0.003 as protection against type I error. For sub aim 2 since we anticipate that many different analyses will be performed (each DNA adduct against each relevant metabolite) we will use a Bonferroni-corrected p-value of  $0.05/50 = 0.001$  to declare significance in these analyses. Detectable effects will correspond to approximately 3 percent of variance of the DNA adducts explained.

**Aim 3:** Identification and quantification of known and previously unknown DNA adducts. This aim has two sub-aims. The first is to identify known and unknown DNA adducts related to smoking status among 50 current smokers and never smokers of single ethnic group (Whites). The second sub aim is to determine ethnic differences in DNA adduct levels found to be elevated in smokers in the first sub-aim. DNA oral cell adducts will be measured in smokers from Core B. Because of cost and time considerations 20 smokers with high levels of the (acrolein and crotonaldehyde) adducts measured in Project 4 Aim 1 will be selected for analysis of sub aim 2.

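### Project 4 Aim 1: the 80% power claimed for 1% ethnicity-by-smoking interactions in 300 smokers needs the other model terms to explain at least 61–68% of adduct variance (alpha 0.05 assumed), and the plan states no such value

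*Combined protocol and SAP*

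**What the plan says.** The claim is in Section 16, Project 4, Aim 1, directly after the power statement for pairwise ethnic comparisons. The plan introduces the analysis with "We can also examine the joint effects of smoking and ethnicity in the total of 300 Core B participants" and says that the study "will have 80 percent power to detect ethnicity x smoking interactions that explain at least an additional 1 percent of variation for any outcome".

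The surrounding text fixes some of the inputs:

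- **Population.** Aim 1 is described as "Evaluation of ethnic differences in DNA adducts in oral cells quantified in 100 smokers from Core B in each of three ethnic groups". Section 5 agrees: "Approximately 300 smokers will be recruited from the Multiethnic Cohort (MEC) study or the general population". Every participant in this analysis is therefore a smoker.
- **Model.** Linear regression is fitted to (possibly transformed) "adduct levels to allow for differences by age, sex, BMI, TNE and CPD while examining ethnic group differences".
- **Not given for the interaction test.** Alpha, sidedness, degrees of freedom, and the variance explained by the other terms.

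Two other statements in Section 16 concern the same 300 smokers. Project 2 Aim 2 gives about 3% of variance as detectable with 80% power. Project 4 Aim 2, sub aim 2, tests at p = 0.001 and says "Detectable effects will correspond to approximately 3 percent of variance of the DNA adducts explained", without stating the power.

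**The concern.** With 300 observations and alpha 0.05, an F test has 80% power for an increment of roughly 3% of total variance when nothing else in the model explains variance. That is what Project 2 Aim 2 reports. An increment of 1% at the same sample size and power is a threefold improvement. It can come only from other terms removing most of the residual variance, or from a much looser test. The plan mentions neither.

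Because all 300 participants smoke, the interaction must be with smoking amount (TNE or CPD), not smoking status. With three ethnic groups, that interaction has 2 df unless a single contrast is specified, and 2 df makes the claim harder to meet. The claim is also made for every outcome, so the condition would have to hold for each adduct in the aim.

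The stake is interpretation. A reader who accepts the sentence would take a null interaction result as good evidence against effects of 1% or more. If the other terms explain 0–50% of variance, the increment actually detectable with 80% power is about 1.3 to 3 times larger.

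**Working it through.** **Inputs**

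- N = 300, power 80%, increment ΔR² = 0.01 (Section 16, Project 4, Aim 1).
- Other model terms: age, sex, BMI, TNE, CPD and two ethnicity indicators, 7 in all (same section).
- Alpha: not stated; two-sided 0.05 assumed, with other values tried below.
- Interaction df: not stated; 2 for three groups by one dose variable, 1 if a single contrast.
- Base R² (variance explained by the other terms): not stated; shown as a range.

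**Method.** Incremental-R² F test:

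- f² = ΔR² / (1 − R²base − ΔR²)
- λ = N × f²
- df = (q, 300 − 1 − 7 − q), i.e. (1, 291) or (2, 290)
- power from the noncentral F distribution

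**Calibration on the plan's own figures.** With base R² = 0, N = 300 and alpha 0.05, the increment detectable at 80% power is 2.6% (1 df) or 3.1% (2 df). This agrees with the roughly 3% in Project 2 Aim 2. The 18% in Project 4 Aim 3 (50 per group, alpha 0.00025) also reproduces, at 17.9%. The method therefore matches the one behind these figures.

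**Power for an additional 1%.** λ = 3 / (0.99 − R²base).

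| Base R² | λ | Power, 1 df | Power, 2 df | Increment detectable at 80%, 1 df / 2 df |
|---|---|---|---|---|
| 0 | 3.03 | 41% | 32% | 2.6% / 3.1% |
| 0.30 | 4.35 | 55% | 44% | 1.8% / 2.2% |
| 0.45 | 5.56 | 65% | 55% | 1.4% / 1.7% |
| 0.50 | 6.12 | 69% | 59% | 1.3% / 1.6% |
| 0.60 | 7.69 | 79% | 70% | 1.0% / 1.3% |
| 0.70 | 10.34 | 89% | 83% | below 1% |

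Simulation (three groups of 100, continuous dose, 6,000 runs per cell) agrees: 39.5%/31.2% at base R² 0, 53.1%/43.2% at 0.30, 69.1%/58.2% at 0.50.

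**Base R² needed for the stated claim.** At alpha 0.05, 80% power requires λ of about 7.90 (1 df) or 9.73 (2 df). Solving λ = 3 / (0.99 − R²base):

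- 1 df: 0.99 − 3/7.90 = 0.61
- 2 df: 0.99 − 3/9.73 = 0.68

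These are minimums for the model without the interaction.

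**Other alphas (1 df / 2 df).** At 0.10 the requirement is 0.51/0.60. At 0.017, the pairwise threshold in Project 3 Aim 1, it is 0.71/0.75.

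**Base R² suggested by Project 4 Aim 2.** If its 3% at p = 0.001 is read as a 1-df test with 80% power (the power is an assumption), the implied base R² is about 0.45. Power for the 1% interaction is then 65%/55%. If the 3% is rounded from 2.5–3.5%, the implied base runs from 0.54 down to 0.36, and power runs from 73% to 59% (1 df) or 63% to 48% (2 df).

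**Participants needed for 1% at 80% power (1 df / 2 df).** 779/957 at base R² 0, 544/668 at 0.30, 387/476 at 0.50.

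**The case against.** The strongest reply is that the claim is unproven, not false. The covariates include two smoking-dose measures, and the documents give no R² for any adduct model, so they do not show that 60% is out of reach. At 60% the 1-df test has 79% power. This stands, and it is why the conclusion is conditional.

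A second reply is that small changes of reading narrow the gap. At a base R² of 45% the 1-df detectable increment is 1.4%, which rounds to 1%. At a base of 54%, a one-sided 1-df test has about 82% power for exactly 1%. But the plan writes 1% as a floor, not an approximation. It specifies neither a one-sided test nor a single contrast, and the natural 2-df test at 45% gives 1.7%. The 45% is itself weak evidence: the Aim 2 sentence states no power, and with base R² = 0 the figure at p = 0.001 would be 5.5%, so that 3% may simply be loose. The Project 2 Aim 2 statement is the firmer comparator.

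Third, Project 4 also uses non-smokers. With 600 people the base R² needed falls to 0.23 (1 df) or 0.37 (2 df). The sentence, however, specifies the 300 Core B participants, all smokers. Even with 600, power is only 69%/59% at base R² 0.

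Finally, this is an additional analysis on which no design choice depends. That limits the importance of the point but does not make the figure reproducible.

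**Conclusion.** The concern holds. The stated 80% power for a 1% interaction cannot be reproduced from anything in the plan. At an assumed two-sided alpha of 0.05 with all 300 participants evaluable, it requires the other terms to explain at least about 61% (1 df) or 68% (2 df) of variance for every adduct outcome. For base R² between 0 and 50%, actual power is 41–69% (1 df) or 32–59% (2 df), and the increment detectable at 80% power is 1.3–2.6% or 1.6–3.1%. The result depends on the assumed alpha: 0.10 would still require 51% or 60%, and a multiplicity-adjusted alpha would require more. The sentence should be corrected. The main Aim 1 ethnic comparison and the sample size are unaffected.

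**What to change.** Revise the one sentence in Section 16, Project 4, Aim 1, in either of two ways:

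- **Restate the increment (preferred).** With 300 smokers, two-sided alpha 0.05 and a 2-df test, there is 80% power for ethnicity-by-smoking-dose interactions that add about 3% of variation, or about 2% if the other model terms explain 30%.
- **Keep 1%.** State alpha and degrees of freedom, and justify a base R² of at least about 61% (1 df) or 68% (2 df) for the adduct outcomes.

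In both cases, say that smoking here means dose among smokers and name the variable (TNE or CPD). The cost is a less favourable stated figure; design, sample size and data collection do not change.

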## Study Synopsis

The Clinical and Biomarkers Core of the Program Project entitled "Mechanisms of Ethnic/Racial Differences in Lung Cancer Due to Cigarette Smoking" will recruit smokers in Hawaii to collect biological samples and will carry out analyses of tobacco constituent biomarkers for four projects. The biological samples collected will be used to evaluate and compare biomarkers of tobacco exposure across Japanese Americans, Whites, and Native Hawaiians on multiple urinary or blood components to assess tobacco related exposures.

The samples will either be procured from the existing biorepository of the Multiethnic Cohort MEC Study for life-long non-smokers or obtained from smokers who are recruited from the MEC or general population by this Core. **This protocol includes the scope of work for the Clinical and Biomarkers Core related to recruitment of human subjects (Observation Study) for the 3 projects that will use and/or store the biorepository samples.** Biorepository samples will be available to the PPG research team or other qualified investigators examining issues related to cancer and/or tobacco exposure biomarkers.

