Volatile compounds such as acrolein and crotonaldehyde may also contribute to lung cancer induction in smokers. Acrolein is a highly toxic agent in cigarette smoke, causing cilia-toxicity among other effects in the lung. One study has shown that acrolein causes a pattern of DNA damage in the p53 tumor suppressor gene similar to that observed in lung tumors of smokers. We have demonstrated the presence of substantial quantities of acrolein-DNA adducts in human lung DNA. Crotonaldehyde, a structural homologue of acrolein, also forms DNA adducts in the human lung, and these are known to be mutagenic, although crotonaldehyde has not been shown to be carcinogenic to the lung. Acrolein and crotonaldehyde are detoxified by reactions with glutathione, and the resulting conjugates are excreted in the urine as 3-hydroxypropylmercapturic acid (3-HPMA) and 3-hydroxy-1-methylpropylmercapturic acid (HMPMA), respectively. These mercapturic acids can be readily measured by established and analytically validated methods, and are related to cigarette smoking. Previous research shows levels of these mercapturic acids were unusually elevated in Native Hawaiians, an aspect that will be further investigated in Project 4.

Cadmium (Cd) is a human lung carcinogen, with cigarette smoking being one of the major sources of exposure. Urinary Cd increases with age and smoking, as major determinants of its levels. A statistically significant association between urinary Cd levels and lung cancer mortality in men from the NHANES III cohort has been reported. While there is some overlap in urinary levels of Cd between smokers and non-smokers, the levels of this biomarker have been demonstrated to increase with smoking. Exposure to Cd has been shown to cause hypermethylation of tumor suppressor genes and was inversely associated with LINE1 methylation, which is a common epigenetic event in carcinogenesis.

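### Project 4, Aim 2, sub aim 1: no planned analysis compares the Native Hawaiian versus Japanese American difference in smokers with the same difference in non-smokers

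*Combined protocol and SAP*

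**What the plan says.** Section 16, Project 4, Aim 2 gives sub aim 1 a main hypothesis in two parts. First, metabolites of acrolein and crotonaldehyde, and markers of oxidative damage and inflammation, are higher in Native Hawaiian (NH) non-smokers than in the other groups. Second, for acrolein and crotonaldehyde, "that this is the reason that acrolein and crotonaldehyde metabolites were higher in Native Hawaiian smokers than Japanese American smokers". The sentence then attributes that smoker difference to a study the team had already published. Section 2 gives the background: "Previous research shows levels of these mercapturic acids were unusually elevated in Native Hawaiians, an aspect that will be further investigated in Project 4".

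The planned analysis compares ethnic groups among non-smokers and among smokers, and adds: "We will also compare smokers to non-smokers from each ethnic group". In summary, "For sub aim 1 we will compare the urinary metabolite levels in each group of 100 with the other groups", and "We will use a p-value for any pairwise comparison of 0.003 as protection against type I error". Ethnic differences are to be estimated after checks for batch effects and transformation to normality. No sample size or power is stated for this sub aim.

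Two neighbouring texts matter. Under Aim 1 (DNA adducts), "We can also examine the joint effects of smoking and ethnicity in the total of 300 Core B participants", and the Aim 1 regression models are fitted "to allow for differences by age, sex, BMI, TNE and CPD while examining ethnic group differences". The Study Synopsis says of sample sources: "The samples will either be procured from the existing biorepository of the Multiethnic Cohort MEC Study for life-long non-smokers or obtained from smokers".

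**The concern.** The second part of the hypothesis compares two differences: NH minus Japanese American (JA) in smokers, and NH minus JA in non-smokers. If background level is the whole explanation, the two should be about equal on a suitable scale. If it explains only part, the smoker difference should be larger. Separate tests of each difference do not test whether they are equal. Both can be significant when background explains half, and one can miss significance when background explains everything.

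Two choices that can change the answer are also open for this sub aim: the scale, which is left to whatever achieves normality, and whether smoking dose (TNE, CPD) is allowed for among smokers. If both are settled after the data are seen, the explanatory conclusion can depend on the choice.

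**Working it through.** **1. The plan's own level.** Three ethnic groups by two smoking strata make six groups, so there are 6×5/2 = 15 pairs. 0.05/15 = 0.0033, which rounds to the stated 0.003. The divisor is not given in the plan, so this is an inference. If it is right, the error control was built for simple pairs only.

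**2. Does the Aim 1 interaction cover the gap?** It uses the 300 Core B participants. Project 2, Aim 2 describes all 300 as smokers, 100 per ethnic group, and the Synopsis takes non-smokers from the existing biorepository. In Aim 1, smoking can therefore only mean amount smoked, and the non-smoker level does not enter. The outcome there is DNA adducts, not urinary metabolites.

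**3. Precision of the missing contrast.** Assumptions: 100 in each of the six groups, independent groups, a common SD of 1, two-sided tests, normal approximation.
- SE of one pairwise difference: √(2/100) = 0.141 SD.
- SE of the contrast (NH − JA in smokers) − (NH − JA in non-smokers): √(4/100) = 0.20 SD, about 1.4 times as large.
- 95% half-width: 1.96 × 0.20 = 0.39 SD.
- Difference detectable with 80% power: (1.960 + 0.842) × 0.20 = 0.56 SD at 0.05; (2.968 + 0.842) × 0.20 = 0.76 SD at 0.003.
- If the smoker SD is k times the non-smoker SD, the SE is √((2 + 2k²)/100): 0.32 for k = 2 and 0.45 for k = 3, in non-smoker SDs.

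**4. What the pairwise pattern shows, and what the contrast shows.** The documents give no effect sizes for these metabolites, so a range is assumed. The one nearby figure is Aim 1's detectable 6% of variance, which for two equal groups is 2√(0.06/0.94) = 0.51 SD.

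Power of one pair at 0.003 is 0.115 (0.25 SD), 0.199 (0.3), 0.715 (0.5), 0.899 (0.6) and about 1.00 (1.2). The chance that both pairs are significant is the product.

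| True NH − JA (non-smokers, smokers) | Background explains | Both pairs at 0.003 | Contrast at 0.05 | Contrast at 0.003 |
|---|---|---|---|---|
| 0.6, 0.6 | all | 0.899² = 81% | 5% | 0.3% |
| 0.6, 1.2 | half | 0.899 × 1.00 = 90% | 85% | 51% |
| 0.3, 0.6 | half | 0.199 × 0.899 = 18% | 32% | 7% |
| 0.5, 0.5 | all | 0.715² = 51% | 5% | 0.3% |
| 0.25, 0.5 | half | 0.115 × 0.715 = 8% | 24% | 4% |

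If background explains everything, smokers alone reach 0.003 in 0.899 × 0.101 = 9% of studies (0.6 SD) or 0.715 × 0.285 = 20% (0.5 SD). That pattern could be misread as evidence against the hypothesis.

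Expected 95% intervals for the contrast are 0.60 ± 0.39 = 0.21 to 0.99 for (0.6, 1.2); 0.25 ± 0.39 = −0.14 to 0.64 for (0.25, 0.5); and 0 ± 0.39 for (0.5, 0.5). Near 0.5 SD the last two overlap heavily, so the data would not settle half versus all. The interval would show this; a list of significant pairs would not.

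**5. Scale and dose (illustrations with assumed values).** Let background be 1.5 in NH and 1.0 in JA, and let smoking add s to both. On the raw scale the non-smoker difference matches 0.5/0.5 = 100% of the smoker difference for any s. On the log scale the share is ln(1.5)/ln((1.5 + s)/(1.0 + s)): 100% at s = 0, 0.405/0.223 = 182% at s = 1, and 0.405/0.118 = 344% at s = 3. Conversely, a proportional loss in stored non-smoker samples moves the raw share from 100% (no loss) to 0.4/0.5 = 80% (20% loss) and leaves the log contrast unchanged. For dose, the contribution to the contrast is the TNE–metabolite correlation times the NH − JA difference in TNE: zero if TNE does not differ, 0.6 × 0.5 = 0.30 SD if those two values held.

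**The case against.** The best defence is that the plan already promises to estimate the ethnic differences and to compare smokers with non-smokers within each group. The contrast is a subtraction of quantities that will be available, and the explanatory clause concerns a difference seen in an earlier dataset, so it can be read as rationale. Most of this stands. What is missing is one named contrast, its interval and its scale. No data are missing, and a contrast in the newly recruited smokers does not directly explain a published difference whose scale and adjustments are not in these documents.

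A reader might also infer that the pairwise results say nothing about the explanation, or that it could be judged only from which pairs reach 0.003. Neither follows. Absence of the non-smoker excess would count against the hypothesis, and estimates are promised. With the smoker difference held at 0.6 or 0.5 SD, the pairwise pattern separates half from full explanation more (18% vs 81%; 8% vs 51%) than the contrast tested at 0.05 does (32% vs 5%; 24% vs 5%). The contrast test is clearly better only when the half-explained smoker difference is as large as 1.2 SD, over twice the plan's 0.51 SD.

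The case for the contrast is therefore as an estimate with an interval for the quantity the hypothesis names. It is not a more powerful test.

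**Conclusion.** The point holds in a limited form. The plan states an explanatory hypothesis and plans no analysis that compares the two ethnic differences or gives the uncertainty of that comparison. This follows from the text and does not depend on the assumed effects.

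The size is minor. It affects one sub aim of one project in a protocol whose own aim is sample collection. The precision figures rest on 100 per group and equal SDs, and would be worse if smokers are more variable. The scale and dose figures are illustrations, not predictions.

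A reader might infer that adding the contrast would establish the reason for the published difference. The documents do not support that. The contrast will often fail to separate partial from full explanation, and it carries any difference between newly collected smoker samples and stored non-smoker samples.

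**What to change.** In Section 16, Project 4, Aim 2, sub aim 1:
- For 3-HPMA and HMPMA, prespecify (NH minus JA in smokers) minus (NH minus JA in non-smokers), reported as an estimate with a 95% confidence interval. Keep the pairwise tests at 0.003.
- State the primary scale in advance: untransformed if background is thought to add, with log as sensitivity analysis, or the reverse with reasons.
- Add a sensitivity analysis allowing for TNE and CPD among smokers.
- State that precision is limited, that a contrast near zero does not show background to be the reason, and that the conclusion will be worded as how much of the new smoker difference is matched by the non-smoker difference.
- Otherwise, limit the stated hypothesis to the non-smoker comparison.

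The cost is a paragraph of text and one contrast per metabolite, with no new participants, samples or assays. The drawback is the wider interval. If the contrast is also to be tested, its significance level should be stated, since the detectable difference depends on it.

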**Statistical Analysis and Power.** For sub aim 1 we will test for differences in DNA adduct levels between smokers and never smokers using parametric or (if appropriate) non-parametric single degree of freedom tests (t-test, Wilcoxon, etc.) Because it is anticipated that several hundred adducts (known + unknown) will be measured we will use a Bonferroni criteria of  $.05/200 = 0.00025$  in order to declare that the observed differences are statistically significant. With 50 participants per group we will be able to detect (with 80 percent power) a smoking difference explaining 18 percent of variation of the adduct level, equivalent to about 1 standard deviation of the within group (smokers, never-smokers) variation of a given DNA adduct.

For sub aim 2 we analyze 20 participants per group and test for ethnic differences in adduct levels for the adducts shown to be elevated in smokers. Our main comparison is between the high risk group (native Hawaiians) and the other groups (Japanese and Whites). Assuming that 50 of the adducts are elevated in smokers we will use a p value of  $0.05/50=.001$  in our hypothesis testing as protection against multiple comparisons. For a given adduct we will be able to detect a difference of about 1.2 standard deviations amounting to 25 percent of variability explained by ethnicity (Native Hawaiian vs Japanese American + White).

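### Project 4, Aim 2 (sub aim 2): about 3 percent of adduct variance is not detectable with 300 smokers at p < 0.001; at 80 percent power it is about 5.5 percent

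*Combined protocol and SAP*

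**What the plan says.** The sub aim is described in Section 16, Project 4, Aim 2: "Sub aim 2 is to relate DNA adducts measured for the 300 participants in Core B to urinary metabolites", among them TNE, total NNAL and the mercapturic acids of acrolein and crotonaldehyde. The method is to "provide linear regression estimates of the relationships between the DNA adducts and metabolites". Because many adduct-metabolite pairs will be tested, the plan adopts a "Bonferroni-corrected p-value of $0.05/50 = 0.001$ to declare significance in these analyses". The next sentence gives the sensitivity: "Detectable effects will correspond to approximately 3 percent of variance of the DNA adducts explained".

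That is all the plan says about what this sub aim can detect. It does not state power, whether the test is one- or two-sided, or which covariates enter the model. Power of 80 percent is named in Project 4, Aim 1 and Aim 3 (sub aim 1), and in Project 2, Aim 2. The last of these also gives about 3 percent for the same 300 smokers, but mentions no multiplicity-corrected threshold.

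**The concern.** The 3 percent follows directly after the 0.001 threshold, so a reader takes it as the effect detectable at that threshold. It is the value one would expect for 300 subjects at a conventional significance level. Moving from 0.05 to 0.001 should raise the detectable share substantially, yet the figure matches the one in Project 2, Aim 2, where no correction is mentioned.

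What is at stake is how null results are read. If 3 percent is taken at face value, a non-significant pair will look like evidence against an association of that size. With power of about 39 percent, a true 3 percent association would be missed about 61 percent of the time (100 − 39), and this applies to every pair tested.

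**Working it through.** **Inputs.** n = 300, alpha = 0.05/50 = 0.001, and a claimed share of variance R² = 0.03, all from Project 4, Aim 2. One degree of freedom per test is inferred from regressing each adduct on each metabolite. Two-sided testing and 80 percent power are assumptions, the latter taken from elsewhere in Section 16. No covariates in the base case.

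**Method.** Noncentral F test of one slope: f² = R²/(1 − Rcov − R²), noncentrality λ = n·f², degrees of freedom 1 and n − 2 − k. Rcov is the share of adduct variance explained by k covariates.

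**Where 3 percent does reproduce.** At n = 300 and alpha = 0.05, the detectable R² at 80 percent power is 2.6 percent (1 df) or 3.1 percent (2 df), and power at 3 percent (1 df) is 86 percent. Setting 80 percent power at 3 percent and solving for alpha gives about 0.028. So the figure fits a test at roughly 0.03 to 0.05.

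**At the stated threshold.**
- For R² = 0.03: f² = 0.03/0.97 = 0.0309 and λ = 300 × 0.0309 = 9.28. Power is 39.3 percent (Fisher-z 39.2 percent; simulation with 40,000 replicates 38.8 percent).
- For 80 percent power: R² = 5.48 percent (Fisher-z 5.54 percent). The normal approximation gives x = (z for 0.001 two-sided + z for 0.80)²/300 = 0.0569 and R² = x/(1 + x) = 5.39 percent.
- For 80 percent power at R² = 3 percent, about 558 subjects would be needed.

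**Varying the unstated conditions (n = 300, alpha = 0.001, no covariates).**

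| Test | Power at 3% | R² at 50% power | R² at 80% power | R² at 90% power |
|---|---|---|---|---|
| Two-sided | 39% | 3.5% | 5.5% | 6.6% |
| One-sided | 47% | 3.1% | 5.0% | 6.1% |

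**Allowing covariates to explain adduct variance (assumed range, two-sided).** Under this formula the detectable share of total variance is 5.48 percent × (1 − Rcov).

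| Rcov | R² at 80% power | Power at 3% |
|---|---|---|
| 10% | 4.9% | 46% |
| 20% | 4.4% | 54% |
| 30% | 3.8% | 63% |
| 40% | 3.3% | 74% |
| 45% | 3.0% | 80% |

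The degrees of freedom used by five to eight covariates make no material difference.

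**Check against other figures in Section 16, at 80 percent power.**

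| Place | n, alpha | Stated | Recomputed |
|---|---|---|---|
| Project 4, Aim 3, sub aim 1 ("a smoking difference explaining 18 percent of variation of the adduct level") | 100, 0.00025 | 18% | 17.9% |
| Project 4, Aim 3, sub aim 2 ("amounting to 25 percent of variability explained by ethnicity"; power not stated there) | 60, 0.001 | 25% | 23.9% |
| Project 3, Aim 3, genome-wide | 40, 2.5 × 10⁻⁸ | 63% | 61.7% |
| Project 3, Aim 3, candidate SNPs | 40, 0.0005 | 38% | 35.6% |
| Project 3, Aim 1 | 200 (two groups), 0.017 | 6% | 5.0% |

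These stated figures are all slightly larger than the calculation, that is, slightly cautious. The 3 percent errs the other way, and by more: 5.48/3 = 1.8.

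**The case against.** The arithmetic is not in dispute; the argument is about what the sentence means. The plan gives no power, sidedness or covariates here, so 5.5 percent rests on imported conditions. Covariate adjustment is also plausible: Project 4, Aim 1 models "adduct levels to allow for differences by age, sex, BMI, TNE and CPD while examining ethnic group differences", and Project 2, Aim 2 adjusts similar regressions for age, sex, BMI and ethnicity. The plan says approximately 3 percent, and anything below 3.5 percent rounds to 3. That needs covariates explaining about 36 percent of adduct variance (5.48 × 0.64 = 3.5), not the full 45 percent.

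Part of this stands. If covariates explained 40 percent, 3.3 percent would be detectable and the stated figure would be a fair rounding. But the plan lists no covariates for this sub aim and assumes no covariate R-squared, so that reading has to be supplied from outside. Relaxing power or sidedness alone does not help: the nearest variant is a one-sided test at 50 percent power (3.1 percent), which the plan nowhere proposes.

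It is also fair to say that agreement elsewhere in Section 16 is uneven. In Project 4, Aim 1, the plan claims that interactions explaining an additional 1 percent are detectable in 300 participants at 80 percent power. At an assumed alpha of 0.05 the same method needs 2.6 percent (1 df) or 3.1 percent (2 df). The comparison with other figures is therefore only supporting evidence; the case rests on the direct recalculation.

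**Conclusion.** The concern holds. With 300 smokers and a two-sided, unadjusted, one-degree-of-freedom test at 0.001, power at 3 percent of variance is about 39 percent, and the share detectable with 80 percent power is about 5.5 percent. The assumptions are the sidedness, the 80 percent power level and the absence of covariates, none of which the plan states for this sub aim. The conclusion weakens only if covariates explain roughly 36 to 45 percent of adduct variance.

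The 3 percent fits an uncorrected significance level, but how it arose cannot be shown from the documents. The consequence is limited: the 0.001 threshold, type I error control and the sample of 300 are unaffected. What needs correcting is one stated sensitivity figure, which matters for reading null results.

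**What to change.** Replace the sentence in Section 16, Project 4, Aim 2 with wording such as:

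> With 300 smokers and a two-sided threshold of 0.001, there is 80 percent power to detect a metabolite that explains about 5.5 percent of the variance of a DNA adduct, before covariate adjustment.

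Alternatively, keep 3 percent and state the power, the sidedness, the covariates and the covariate R-squared on which it rests. Leave the threshold and the sample size as they are. The cost is one sentence and a less favourable stated sensitivity.
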